- a. **Post-Operative Surveys:** A short survey will be administered to the surgeon following completion of each Intervention Case (“*Post-Operative Surveys*”). The survey will include questions regarding the Primary Endpoints (as measured on a Likert-type scale), and the helpfulness of the VR Models during case planning. No PHI will be reflected or gathered in these surveys.
- b. **Surgeon Experience Surveys:** Surgeon experience surveys will be administered with each participating surgeon two times during study: The first one after the surgeon has completed 5 Intervention Cases, and the second one at the completion of the study (“*Surgeon Experience Surveys*”). No PHI will be gathered or reflected in these surveys. Initial list of questions set forth on **Exhibit B**.
- c. **Purpose.** The Post-Operative Surveys and Surgeon Experience Surveys will be used by the researchers to further assess whether and to what degree the VR Models:
 - i. Impact the surgeons’ understanding of their patients’ anatomy;
 - ii. Impact the surgeons’ confidence in their preoperative plans;
 - iii. Impact the surgeons’ accuracy in their preoperative plans;
 - iv. Impact the surgeons’ efficiency in their intraoperative execution;
 - v. Are perceived as particularly beneficial in cases with any specific anatomical characteristics;
 - vi. Are perceived as particularly beneficial to any specific surgery types; and
 - vii. Are perceived as more or less helpful when viewed in VR format as opposed to regular 3D format.

VI. HOSPITAL PARTICIPANTS AND RESPONSIBILITIES

- a. **Principal Investigator (PI)**
 - i. Overall point person for study.
 - ii. Coordinates support for study with other participants, including Research Coordinator and surgeon users.
- b. **Research Coordinator (“RC”):**
 - i. Identify, collect and manage:
 - The CTs and MRIs from which the VR Models will be created by Ceevra
 - Data regarding Control Cases (“**Control Case Data**”) and Intervention Cases (“**Intervention Case Data**”)
 - ii. Deidentify each source CT/MRI using deidentifying software (or ensures that Radiology deidentifies the image prior to delivery to the RC); deliver the deidentified image to Ceevra along with a unique identifier.
 - iii. Coordinate with surgeon users to ensure that both the VR model and the underlying CT/MRI are reviewed prior to operation.

- iv. Assist with administration of the Post-Operative Surveys and the Surgeon Experience Surveys.
- c. **Surgeon Users.** Key activities:

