Post-Op Complications	Yes/No	✓
Readmissions	Yes/No	✓
Intervention Case Sample Size		
		39

EXHIBIT B
SURGEON EXPERIENCE SURVEY QUESTIONS

1. How likely are you to recommend the VR Models to other surgeons in your department (scale 0-5, with 0 being “I would recommend against use of the VR Models”; 1 being “I am not ready to make any recommendation”; and 5 being “I would definitely recommend the VR models to other surgeons in my department”)
2. How would you rate the “imaging quality” of the VR model. For imaging quality, consider aspects such as detail, resolution, color, translucency (scale 0-5, with 1 being Very Poor and 5 being Excellent).
3. How would you rate the “viewing experience” of the VR model. For viewing experience, consider elements such as depth, angle, ability to rotate model, ability to zoom in/out, ability to show/hide anatomical parts. Same answer scale as Question 2.
4. How much did the VR model impact your confidence in your pre-operative surgical plans. (scale 0-5, with 0 being “Using the VR Model made me feel less confident” and 5 being “Using the VR Model made me feel significantly more confident”)
5. How much did the VR model improve your understanding of the patient’s anatomy. (scale 0-5, with 0 being “The VR Model did not improve my understanding of the patient’s anatomy or was confusing” and 5 being “The VR Model significantly improved my understanding of the patient’s anatomy”)
6. What did you like best about the VR model as compared to the CT/MRI (Choices: I did not like any aspects of the VR model; ease of access/viewing from mobile phone; imaging quality; viewing experience; ability to see entire operating site in one view vs. multiple views axial/coronal/sagittal; other)
7. What recommendations do you have for improving the VR models or the viewing experience.
8. Please identify any key anatomical parts that you feel are missing from the model.
9. How helpful is accessing and viewing the image from your own mobile phone or tablet (as compared to viewing images from computer or workstation) (scale 0-5, with 0 being not very helpful and 5 being extremely helpful)

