10. How helpful is viewing the image in Virtual Reality mode (as compared to viewing image in regular 3D mode) (scale 0-5, with 0 being “It was less helpful to view the image in Virtual Reality Mode than it was to view it in regular 3D mode” and 5 being “It was extremely helpful to view the image in Virtual Reality mode as opposed to only viewing it in regular 3D mode”)
11. If you answered 0 or 5 to Question 10, provide detail as to why.

EXHIBIT C

EXAMPLE CASE OUTCOMES DATA FIELDS

Outcomes Data categories for Partial Nephrectomy:

- Preoperative parameters
 - Age
 - Sex
 - Race
 - 1 or 2 kidneys
 - Kidney side (R vs L)
 - Tumor size (cm)
 - Tumor location (upper, lower, middle pole)
 - Tumor orientation (anterior or posterior)
 - Percentage of tumor protruding (% endophytic)
 - Tumor density (% solid)
 - Nephrometry score, with modifier for multiple tumors
- Surgical technique
 - Case type (robotic partial)
 - Surgical approach (transperitoneal; retroperitoneal)
 - 4th Robotic arm used (y/n)
 - Arteries clamped (0-4)
 - Veins clamped (0-4)
 - Ultrasound used (y/n)
 - Firefly used (y/n)
- Case Outcomes
 - Tumor localization time
 - Tumor resection time
 - Reconstruction time
 - Total operative time
 - Blood Loss (cc)
 - Clamp time (mins)
 - Conversion to open (y/n)
 - Conversion to radical (y/n)
 - Operative complication (y/n)
- Post-op Outcomes
 - Hospital stay (days)
 - Positive margins (y/n)
 - Post-op complication
 - Readmission

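### Several Surgeon Experience Survey scales are unbalanced or incompletely labelled, so no effect, harm and modest benefit cannot be cleanly told apart

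*Combined protocol and SAP*

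**What the plan says.** Section V.b has each participating surgeon complete the survey twice, after five Intervention Cases and at study completion, and describes the question list as initial. Section V.c uses it, together with the Post-Operative Surveys, to judge whether and how far the VR Models affect understanding of anatomy (i) and confidence in the plan (ii), among other things. Purpose (vii) is whether they "Are perceived as more or less helpful when viewed in VR format as opposed to regular 3D format".

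The scaled items in Exhibit B run from 0 to 5:

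- Item 1 (recommendation): 0 is "I would recommend against use of the VR Models", 1 is "I am not ready to make any recommendation", 5 is "I would definitely recommend the VR models to other surgeons in my department".
- Items 2 and 3 (imaging quality, viewing experience): "scale 0-5, with 1 being Very Poor and 5 being Excellent". Item 3 takes its scale from item 2.
- Item 4 (confidence): 0 is "Using the VR Model made me feel less confident"; 5 is a significant gain in confidence.
- Item 5 (understanding): 0 is "The VR Model did not improve my understanding of the patient’s anatomy or was confusing"; 5 is a significant improvement.
- Item 10 (VR mode against regular 3D): 0 is "It was less helpful to view the image in Virtual Reality Mode than it was to view it in regular 3D mode"; 5 is extreme helpfulness of VR mode.

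Item 9 (own phone or tablet against workstation) is also scaled. Items 6 to 8 and 11 are choice or free-text questions.

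**The concern.** A question about whether something had an effect needs a score that means no effect. A question about degree, where the effect could go either way, needs grades on both sides of that score. Items 4, 5 and 10 correspond directly to purposes (ii), (i) and (vii) of section V.c, and none of them has a score that means only no effect. Purpose (vii) is worded as two-sided, but item 10 labels a single negative point and offers no label for equality.

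Item 5 deserves the most attention. Section I.a gives better understanding of anatomy as the route by which VR is expected to help. Exhibit A measures times and clinical outcomes, not understanding, and section V.a describes the Post-Operative Survey as covering the primary endpoints and helpfulness in planning. Item 5 is therefore the only question printed in the documents that asks about understanding directly. If a surgeon answers 0, nobody can tell afterwards whether the model was merely unhelpful or actually misleading.

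**Working it through.** The documents state no figure for this survey, so there is nothing to reproduce. The check counts what each score means.

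Inputs: the labels in Exhibit B; four surgeons (section IV.d); two administrations per surgeon (sections V.b and VIII.d); 39 Intervention Cases (Exhibit A).

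**Item 1.** The plan itself fixes neutral at 1. Below neutral: {0}, one grade. Above neutral: {2, 3, 4, 5}, four grades. Neutral lies at 1/5 = 20% of the range. The arithmetic middle is (0 + 5)/2 = 2.5, which is 2.5 − 1 = 1.5 points above neutral. An answer near the middle of this scale is already on the favourable side.

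**Item 5.** Scores 1 to 5 can be read as increasing improvement. Score 0 holds both no improvement and confusion. No score means harm alone and none means no effect alone.

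**Items 4 and 10.** Only 0 (negative) and 5 (strongly positive) are labelled. The low label has no intensifier and the high label has one. Where neutral falls is left to the respondent, so it has to be assumed:

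| Assumed neutral | Scores below | Scores above |
|---|---|---|
| 1 | 1 | 4 |
| 2 | 2 | 3 |
| 2.5 | 3 | 3 |
| 3 | 3 | 2 |

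A score of 2 is favourable in the first row, neutral in the second and unfavourable in the last two. Scores 1 to 4 therefore cannot be classified from the text.

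**Items 2 and 3.** There are six permitted scores, two of them labelled. The worst label sits at 1, so 0 can be chosen but has no meaning.

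**Extent.** The scaled items are 1, 2, 3, 4, 5, 9 and 10, seven in all. Items 1 to 5 and 10, six of the seven, have one of these faults. Item 9 also makes a comparison without a label for equal, but no purpose in section V.c depends on it.

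**Amount of data.** 4 surgeons × 2 administrations = 8 forms.

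**The case against.** The survey does let a surgeon answer negatively. Score 0 is an explicit negative on items 1, 4 and 10. Item 6 offers a choice for disliking everything about the model, items 7 and 8 invite criticism, and item 11 asks for reasons after a 0 on item 10. This stands. A reader might infer that the survey cannot show a negative impact; the documents do not support that. What is missing is any grading of a negative view and, on item 5, any way to isolate it.

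A reader might also infer that the scales lean towards VR throughout. That does not hold either. Neutral is fixed near the bottom only in item 1. No effect is merged with harm only in item 5. For items 4 and 10 even the direction of a lean depends on where the respondent puts neutral, as the table shows. Items 2 and 3 are quality ratings with an undefined 0, which creates no lean. Four of six scores (67%) lie above neutral on item 1 and five of six (83%) above 0 on item 5, but these shares count options and do not predict answers. Section IV.e plans no mean or test for the survey, so a distorted mean cannot be charged to the plan.

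Finally, the Post-Operative Surveys follow every Intervention Case, 39 as planned, and will supply more responses than the 8 forms. That is fair, and it lowers the importance. As described, however, they do not cover understanding, confidence or VR against regular 3D, so they do not replace items 4, 5 and 10.

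**Conclusion.** The point holds as a fault of measurement in a supportive instrument. Used as printed, items 4, 5 and 10 cannot cleanly answer purposes (ii), (i) and (vii) of section V.c; item 1 is unbalanced by its own labels; and items 2 and 3 contain a meaningless score. For items 1 and 5 and for items 2 and 3 this follows from the labels alone. For items 4 and 10 it rests on the absence of any label between 0 and 5, and no direction of bias is claimed.

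Importance is low. The survey is not among the Exhibit A endpoints and about 8 forms are expected, so no conclusion on operative time, clinical outcome or safety depends on it. What changes is what may be said about the surgeons' understanding, confidence and preference for VR format.

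**What to change.** Before the first survey is given, revise Exhibit B as follows:

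- Items 1, 4, 5 and 10: use a symmetric scale with a labelled neutral midpoint and separate negative categories, for example five points from −2 (much worse or much less) through 0 (no difference) to +2 (much better or much more). On item 5, word the question neutrally and keep confusion apart from no change.
- Items 2 and 3: set the range to 1-5 so that it matches the labels.
- Item 11: change the trigger to the two ends of the new item 10 scale.
- Reporting: state that the number of answers in each category will be given for each administration. With 8 forms these counts can be shown in full.

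The −2 to +2 format is one reasonable choice; any scale with equal grades on both sides and a labelled neutral point would serve.

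The cost is rewording one exhibit that section V.b already treats as provisional, with no added visits, staff or patients. The one drawback is lost comparability with any survey already completed on the present scale; such forms should be tabulated separately.
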